8.3 Storage requirements

Dispense in a tight, light-resistant container as defined in the USP/NF.

Store at 20° - 25°C (68° - 77°F) excursions permitted to 15° - 30°C (59° - 86°F) [See USP Controlled Room Temperature].

Store out of the reach of children.

8.4 Stability:

When stored as listed above and light-resistant containers, hydroxychloroquine is stable for 3 years from manufacture date.

8.5 Route of administration:

Hydroxychloroquine is taken orally daily, each dose to be taken with a meal or a glass of milk.

8.6 CONTRAINDICATIONS

Use of this drug is contraindicated (1) in the presence of retinal or visual field changes attributable to any 4-aminoquinoline compound, (2) in patients with known hypersensitivity to 4-aminoquinoline compounds, and (3) for long-term therapy in children.

8.7 Precautions: General

Antimalarial compounds should be used with caution in patients with hepatic disease or alcoholism or in conjunction with known hepatotoxic drugs. Periodic blood cell counts should be made if patients are given prolonged therapy. If any severe blood disorder appears which is not attributable to the disease under treatment, discontinuation of the drug should be considered. The drug should be administered with caution in patients having G-6-PD (glucose-6-phosphate dehydrogenase) deficiency.

8.8 Overdose

Overdose with the 4-aminoquinolines is dangerous particularly in infants, as little as 1-2 grams having proved fatal.

8.9 Symptoms of Overdose:

The 4-aminoquinoline compounds are very rapidly and completely absorbed following ingestion and in accidental overdosage toxic symptoms may occur within 30 minutes. These consist of headache, drowsiness, visual disturbances, cardiovascular collapse, hypokalemia and convulsions, rhythm and conduction disorders, including QT prolongation, torsade de pointes, ventricular tachycardia and ventricular fibrillation, followed by sudden potentially fatal respiratory and cardiac arrest. Immediate medical attention is required, as these effects may appear shortly after overdose. The ECG may reveal atrial standstill, nodal rhythm, prolonged intraventricular conduction time, and progressive bradycardia leading to ventricular fibrillation and/or arrest.

8.10 Treatment of Overdose:

Treatment is symptomatic and must be prompt with immediate evacuation of the stomach by emesis (at home, before transportation to the hospital), or gastric lavage until the stomach is completely emptied. If finely powdered activated charcoal is introduced by the stomach tube, after lavage and within 30 minutes after ingestion of the tablets, it may inhibit further intestinal absorption of the drug. To be effective, the dose of activated charcoal should be at least five times the estimated dose of ingested hydroxychloroquine. Convulsions, if present, should be controlled before attempting gastric lavage. If due to cerebral stimulation, cautious administration of an ultrashort-acting barbiturate may be tried but, if due to anoxia, convulsions should be corrected by oxygen administration, artificial respiration or, in shock with hypotension, by vasopressor therapy. Because of the importance of supporting respiration, tracheal intubation or tracheostomy, followed by gastric lavage, has also been advised. Exchange transfusions have been used to reduce the level of 4-aminoquinolines in the blood. Consideration should be given to administering diazepam parenterally since studies have reported it beneficial in reversing chloroquine cardiotoxicity.

A patient who survives the acute phase and is asymptomatic should be closely observed for at least 6 hours. Fluids may be forced, and sufficient ammonium chloride may be administered for a few days to acidify the urine to help promote urinary excretion.

If serious toxic symptoms occur from overdosage or sensitivity, it has been suggested that ammonium chloride (8 g daily in divided doses for adults) three or four days a week be administered for several months after therapy has been stopped, as acidification of the urine increases renal excretion of the 4-aminoquinoline compounds by 20 to 90 percent. However, caution must be exercised in patients with impaired renal function and/or metabolic acidosis.

9. BIOMARKER, CORRELATIVE, AND SPECIAL STUDIES

9.1 Laboratory Correlative Studies

The plasma concentrations of PAR-4 will be measured to assess induction of PAR-4 in each patient.

The plasma concentration of hydroxychloroquine and its metabolites will also be measured to establish exposure – response (PAR-4 release) relationships. The extra aliquots of plasma after above studies will be stored in –80°C for future biomarker studies if needed.

Blood collection for PAR-4

Collection of Specimens

Blood plasma samples will be collected pre-dosing, and weekly during the preoperative period (+/- 1 day), as well as on or after surgery (+/- 1 day). A total of 8 time points will be required for each patient. 4 ml of venous blood will be withdrawn for pharmacokinetics; 4 ml of venous blood will be withdrawn for Par-4 and biomarker studies. Samples will be withdrawn into

sodium heparinized collection tube.

Handling of Specimens

After collection, blood and anti-coagulant will be mixed by inverting the tube 8–10 times. Blood samples will be placed on ice immediately and centrifuged within 30 min at 7200 g at 4°C for 2 min. Plasma will be transferred into amber plastic tubes and stored on dry ice prior to transferring at –80°C until analysis. Plasma concentrations of PAR-4 will be quantified using ELISA (according to manufacturer’s instruction with a kit from CUSABIO). Moreover, Western blot analysis will be performed as described previously^{2,12} to further confirm the quantitative increase in the ~40 kDa PAR-4 band. Aliquots of plasma samples will be subjected to SDS-PAGE to resolve the plasma proteins. The proteins will be transferred onto nylon membranes, and then subjected to Western blot analysis. The blots will be probed with PAR-4 polyclonal antibody (from SantaCruz Biotechnology, Inc.) Parallel SDS-PAGE and Coomassie blue staining of the albumin in the serum samples will be used as loading control^{2,6}.

Blood Collection and Handling of Specimens for Pharmacokinetics

Blood samples for pharmacokinetic analysis will be collected prior to the start of HCQ regimen and during day 1 of weeks 1 and 2 and on/after day of surgery (+/- 1 day), as specified in the Study Calendar. Blood samples (4 mL) will be collected in heparinized tubes. After collection, blood and anti-coagulant will be mixed by inverting the tube 8–10 times and samples will be placed on ice immediately. Further processing will be carried out in the bioanalytical lab by staff in the Center of Pharmaceutical Research and Innovation (CPRI) under the direction of [name]. Concentrations of HCQ and metabolites will be quantified using a validated bioanalytical assay implemented for LC/MS/MS.

Shipping of Specimens for Pharmacokinetics

Samples will be collected by study personnel and will be forwarded to the CPRI for storage, processing and analysis.

Tumor Collection for Pharmacodynamics

If available, Diagnostic biopsies and paired resected tumor specimen will be store in formalin-fixed, paraffin-embedded blocks for potential autophagy and apoptosis analysis in the future. Each subject will sign the consent form for tissue collection before enrolled in the study.

Shipping of Specimens for Pharmacodynamics

Samples will be collected by study personnel in [name] lab for storage, processing and analysis. For PK/Par-4 sample pick up contact [name] at [contact].

Site(s) Performing Correlative Study

University of Kentucky.

STUDY CALENDAR

Baseline evaluations are to be conducted within 2-4 weeks prior to start of protocol therapy. In the event that the patient's condition is deteriorating, laboratory evaluations should be repeated more frequently, as clinically indicated. Study drug administration should begin optimally 2 weeks prior to date of surgery and continue until day prior to surgery. Dosing can be extended one week if necessary for any unanticipated delays.

| Studies to be obtained | Pre-Study | Week 1 (D7) | Week 2 (D14) | Day of Surgery | Post-operative visit | Off study |
|---|------------------|--------------------|---------------------|-----------------------|-----------------------------|------------------|
| History | X | X | X | | X | X |
| Physical Exam with vital signs | X | X | X | | X | |
| Height, Weight | X | | | | | |
| Performance Status | X | | | | | |
| CBC, differential, platelets | X | X | X | | X | |
| CMP | X | X | X | | X | |
| Pregnancy test (only females of childbearing potential) | X | | | | | |
| Tumor collection for Correlative Studies (if available) | X | | | X | | |
| Correlative Blood work* | X | X | X | | X | |

Correlative Par-4, and Hydroxychloroquine levels will be as follows:

| Date | Lab Draw | Tubes |
|-----------------------------|--|--|
| Pre-study | once | Par-4 (1 tube) Hydroxychloroquine (1 tube) |
| Week 1 (day 7) | 3 samples (2 hours apart +/- 15 minutes) | Par-4 (1 tube) HCQ (3 tubes total- two hours apart) |
| Week 2 (day 14) | 3 samples (2 hours apart +/- 15 minutes) | Par-4 (1 tube) HCQ (3 tubes total- two hours apart) |
| Post-operative clinic visit | once | Par-4 (1 tube), HCQ (1 tube) |

10. DATA REPORTING / REGULATORY REQUIREMENTS

Adverse event lists, guidelines, and instructions for AE reporting can be found in Section 7.0 (Adverse Events: List and Reporting Requirements).

10.1 Data Reporting

10.1.1 Method

This study will require data submission and reporting via the OnCore Database, which is the official database of the Markey Cancer Center Clinical Research and Data Management Shared Resource Facility (CRDM SRF). Instructions for submitting data is listed in Study-Specific Data Management Plans created by CRDM SRF staff.

10.1.2 Responsibility for Data Submission

Study staff is responsible for submitting study data and/or data forms to OnCore as per the Markey Cancer Center CRDM SRF SOP's. This trial will be monitored by the MCC Data and Safety Monitoring Committee (DSMC) on a schedule determined by the Protocol Review and Monitoring Committee at the initial PRMC review. The CRDM SRF staff is responsible for compiling and submitting data for all participants and for providing the data to the Principal Investigator for review.

2. Let j^t denote the highest level tried thus far. At the current dose level j , based on the observed data, determine the dose j^* that has the highest isotonic estimate of biological effect probability among the tried doses.
3. If $j^* > j$, we escalate to dose $j+1$
4. If $j^* < j$, we de-escalate to dose $j-1$
5. If $j^* = j < j^t$, we stay at dose level j ; otherwise if $j^* = j = j^t$, we escalate to dose $j+1$
6. Once the maximum sample size is reached, we select the lowest dose that has the highest estimate of biological effect based on PAR-4 levels. Decisions on the dose that will be utilized for subsequent trials will be based on biological, clinical and statistical considerations.

Table 1. Selection Probabilities for Varying Scenarios of Biological Effect and Toxicity Rates

| | | | | |
|-------------------------|---------|--------|--------|--------|
| Scenario 1 | Dose -1 | Dose 1 | Dose 2 | Dose 3 |
| Biological rates | 0.40 | 0.70 | 0.60 | 0.50 |
| Toxicity rates | 0.02 | 0.05 | 0.10 | 0.20 |
| Selection Probabilities | 8.9 | 53.3 | 28.5 | 9.3 |
| Scenario 2 | Dose -1 | Dose 1 | Dose 2 | Dose 3 |
| Biological rates | 0.40 | 0.60 | 0.75 | 0.55 |
| Toxicity rates | 0.02 | 0.05 | 0.10 | 0.20 |
| Selection Probabilities | 15.5 | 24.0 | 49.1 | 11.4 |
| Scenario 3 | Dose -1 | Dose 1 | Dose 2 | Dose 3 |
| Biological rates | 0.70 | 0.50 | 0.30 | 0.20 |
| Toxicity rates | 0.02 | 0.05 | 0.10 | 0.20 |
| Selection Probabilities | 69.8 | 24.4 | 5.2 | 0.6 |
| Scenario 4 | Dose -1 | Dose 1 | Dose 2 | Dose 3 |

| | | | | |
|-------------------------|---------|--------|--------|--------|
| Biological rates | 0.20 | 0.50 | 0.75 | 0.70 |
| Toxicity rates | 0.02 | 0.05 | 0.10 | 0.20 |
| Selection Probabilities | 9.8 | 13.7 | 46.9 | 29.6 |
| Scenario 5 | Dose -1 | Dose 1 | Dose 2 | Dose 3 |
| Biological rates | 0.20 | 0.50 | 0.70 | 0.70 |
| Toxicity rates | 0.05 | 0.10 | 0.20 | 0.40 |
| Selection Probabilities | 9.9 | 22.2 | 50.7 | 17.2 |
| Scenario 6 | Dose -1 | Dose 1 | Dose 2 | Dose 3 |
| Biological rates | 0.40 | 0.70 | 0.60 | 0.50 |
| Toxicity rates | 0.05 | 0.10 | 0.20 | 0.40 |
| Selection Probabilities | 9.9 | 55.1 | 30.8 | 4.2 |
| Scenario 7 | Dose -1 | Dose 1 | Dose 2 | Dose 3 |
| Biological rates | 0.40 | 0.60 | 0.75 | 0.55 |
| Toxicity rates | 0.05 | 0.10 | 0.20 | 0.40 |
| Selection Probabilities | 15.7 | 27.2 | 50.9 | 6.2 |
| Scenario 8 | Dose -1 | Dose 1 | Dose 2 | Dose 3 |
| Biological rates | 0.70 | 0.50 | 0.30 | 0.20 |
| Toxicity rates | 0.05 | 0.10 | 0.20 | 0.40 |
| Selection Probabilities | 71.2 | 23.6 | 4.5 | 0.7 |
| Scenario 9 | Dose -1 | Dose 1 | Dose 2 | Dose 3 |
| Biological rates | 0.20 | 0.60 | 0.50 | 0.40 |
| Toxicity rates | 0.02 | 0.05 | 0.10 | 0.20 |
| Selection Probabilities | 4.6 | 53.6 | 31.4 | 10.4 |
| Scenario 10 | Dose -1 | Dose 1 | Dose 2 | Dose 3 |
| Biological rates | 0.20 | 0.30 | 0.60 | 0.50 |
| Toxicity rates | 0.05 | 0.10 | 0.20 | 0.40 |
| Selection Probabilities | 20.0 | 16.2 | 52.6 | 11.2 |

11.2 Sample Size/Accrual Rate

A total of 18 patients will be enrolled in cohorts of 3 and dose escalation or de-escalation will be implemented as described in section 12.1 above. We expect to enroll 1 patient per month for expected study duration of 18 months.

11.3 Assessment of Safety

The isotonic regression design as described in 12.1 incorporates toxicity assessment. The dose with the highest selection probability accounts for both the dose with the highest biological effect and toxicity that is closest to the target rate of 30%.

11.4 Stratification Factors

Not applicable for this trial

11.5 Analysis of Safety

All patients who received study drug will be included in the safety analysis of this study. Adverse event data and corresponding toxicity grades during the days of treatment will be summarized in each tumor cohort and in the overall patient population. Incidence tables will be generated to summarize incidence of patients reporting at least one episode of each specific adverse event, incidence of adverse events causing withdrawal and incidence of serious adverse events. The total number of episodes for each event reported (Frequency Table), the severity and attribution to study therapy of each episode reported (Severity Table and Attribution Table) will also be displayed.

Listings of adverse events by patients will include the time to onset, the duration of each event, the severity of each event, and the relationship of the event to study therapy, whether it was a serious event, and whether it caused withdrawal. Safety data will be summarized for the overall patient group and by tumor cohort. Toxicities will be graded according to Common Toxicity Criteria (CTCAE) v4.0.

11.6 Pharmacokinetics Modeling and Pharmacodynamics Analysis

For assessment of biological effect, we will utilize PAR-4 levels from pre-treatment and PAR-4 from the last time point prior to resection. Changes in quantitative levels of PAR-4 measured via ELISA and Western Blot will be calculated and the proportion of patients exhibiting at least a 2-fold induction will be estimated overall and in each dose level along with exact 95% binomial confidence intervals. Isotonic regression will be fitted for the total sample to obtain estimates of biological effect at each dose level. Other exploratory analyses will include: paired tests to evaluate changes in PAR-4 quantitative levels from baseline and at each time point of measurement; correlations between several biological markers indicated in Section 9.1 for Correlative Studies will be estimated using Pearson or Spearman's correlation coefficient; repeated measures modeling of several biomarker measurements over time; and descriptive statistics of biomarker levels for each disease group (if there are enough in each disease site). Similar analyses plans will be employed for biomarker assessments in tissue specimens.

Population pharmacokinetic studies have previously been conducted¹⁵. This will allow the use of population parameters to be used as priors and thus enable forecasting the HCQ exposure for each patient, using a Bayesian approach, despite the limited sampling strategy^{16,17}. Data analysis will be carried out with ADAPT V¹⁸.

11.7 Data Management

The study statistician and staff from the Biostatistics Shared Resource Facility (BSRF) of the Markey Cancer Center will work closely with the study PI and the Clinical Protocol and and Data Management (CPDM SRF) at Markey in the development of eCRFs for the study.

Specifically, the statisticians will attend several meetings including the Protocol Initiation Meeting (PIM) to address all statistical considerations for this protocol including incorporation of dose-escalation and de-escalation plans for the adaptive design in this Phase I trial, appropriate and accurate collection of primary and secondary study endpoints and inclusion of valid values and range checks for data fields. The OnCore clinical trial management system, managed by Markey's CPDM, will be the primary database repository of clinical data from all patients enrolled into this trial. Data will be accessed by the study statistical on a regularly-scheduled basis to perform statistical programming for conduct of data quality control, data management, generation of interim reports and statistical analysis. The BSRF has developed an automated mechanism for generating a trigger for assessment of biological response as well as dose limiting toxicities based on the dose escalation rules in section 12.1 above. In collaboration with the study team, procedures will be developed for timelines for data quality control, resolution of data queries, interim reporting and final data analysis.

APPENDIX A PERFORMANCE STATUS CRITERIA

| ECOG Performance Status Scale | | Karnofsky Performance Scale | |
|-------------------------------|---|-----------------------------|--|
| Grade | Descriptions | Percent | Description |
| 0 | Normal activity. Fully active, able to carry on all pre-disease performance without restriction. | 100 | Normal, no complaints, no evidence of disease. |
| | | 90 | Able to carry on normal activity; minor signs or symptoms of disease. |
| 1 | Symptoms, but ambulatory. Restricted in physically strenuous activity, but ambulatory and able to carry out work of a light or sedentary nature (e.g., light housework, office work). | 80 | Normal activity with effort; some signs or symptoms of disease. |
| | | 70 | Cares for self, unable to carry on normal activity or to do active work. |
| 2 | In bed <50% of the time. Ambulatory and capable of all self-care, but unable to carry out any work activities. Up and about more than 50% of waking hours. | 60 | Requires occasional assistance, but is able to care for most of his/her needs. |
| | | 50 | Requires considerable assistance and frequent medical care. |
| 3 | In bed >50% of the time. Capable of only limited self-care, confined to bed or chair more than 50% of waking hours. | 40 | Disabled, requires special care and assistance. |
| | | 30 | Severely disabled, hospitalization indicated. Death not imminent. |
| 4 | 100% bedridden. Completely disabled. Cannot carry on any self-care. Totally confined to bed or chair. | 20 | Very sick, hospitalization indicated. Death not imminent. |
| | | 10 | Moribund, fatal processes progressing rapidly. |
| 5 | Dead. | 0 | Dead. |

APPENDIX B INFORMATION ON POSSIBLE DRUG INTERACTIONS

A table with potential drug interaction with HYDROXYCHLOROQUINE is included below. HYDROXYCHLOROQUINE should also be used with caution in patients taking medicines which may cause adverse ocular or skin reactions.

Drug Interaction:

| Proper Name | Effect/clinical comment |
|--|---|
| Agalsidase | There is a theoretical risk of inhibition of intra-cellular α -galactosidase activity when HYDROXYCHLOROQUINE is co-administered with agalsidase. |
| Aminoglycoside antibiotics | HYDROXYCHLOROQUINE may also be subject to several of the known interactions of chloroquine even though specific reports have not appeared including potentiation of its direct blocking action at the neuromuscular junction by aminoglycoside antibiotics. |
| Amiodarone | There may be an increased risk of inducing ventricular arrhythmias if HYDROXYCHLOROQUINE is used concomitantly with other arrhythmogenic drugs. |
| Antacids | As with chloroquine, antacids may reduce absorption of HYDROXYCHLOROQUINE so it is advised that a 4 hour interval be observed between HYDROXYCHLOROQUINE and antacid dosing. |
| Anti-diabetic drugs | May enhance the effects of a hypoglycemic treatment, a decrease in doses of antidiabetic drugs may be required. |
| Antiepileptic drugs | The activity of antiepileptic drugs might be impaired if co-administered with HYDROXYCHLOROQUINE. |
| Antimalarials known to lower the convulsion threshold | HYDROXYCHLOROQUINE can lower the convulsive threshold. Co-administration of HYDROXYCHLOROQUINE with other antimalarials known to lower the convulsion threshold (e.g. mefloquine) may increase the risk of convulsions. |
| Arrhythmogenic drugs | There may be an increased risk of inducing ventricular arrhythmias if HYDROXYCHLOROQUINE is used concomitantly with other arrhythmogenic drugs. |
| Cyclosporine | An increased plasma ciclosporin level was reported when ciclosporin and HYDROXYCHLOROQUINE were co-administered. |
| Cimetidine | HYDROXYCHLOROQUINE may also be subject to several of the known interactions of chloroquine even though specific reports have not appeared including inhibition of its metabolism by cimetidine which may increase plasma concentration of the antimalarial. |

| | |
|---|--|
| Digoxin | May result in increased serum digoxin levels; serum digoxin levels should be closely monitored in patients receiving concomitant treatment. |
| Insulin | May enhance the effects of a hypoglycemic treatment, a decrease in doses of insulin may be required. |
| Mefloquine | HYDROXYCHLOROQUINE can lower the convulsive threshold. Co-administration of HYDROXYCHLOROQUINE with other antimalarials known to lower the convulsion threshold (e.g. mefloquine) may increase the risk of convulsions. |
| Moxifloxacin | There may be an increased risk of inducing ventricular arrhythmias if HYDROXYCHLOROQUINE is used concomitantly with other arrhythmogenic drugs. |
| Neostigmine | HYDROXYCHLOROQUINE may also be subject to several of the known interactions of chloroquine even though specific reports have not appeared including antagonism of effect of neostigmine. |
| Praziquantel | Chloroquine has been reported to reduce the bioavailability of praziquantel. Due to the similarities in structure and pharmacokinetic parameters between hydroxychloroquine and chloroquine, a similar effect may be expected for HYDROXYCHLOROQUINE. |
| Pyridostigmine | HYDROXYCHLOROQUINE may also be subject to several of the known interactions of chloroquine even though specific reports have not appeared including antagonism of effect of pyridostigmine. |
| Vaccine: Human diploid cell rabies vaccine | HYDROXYCHLOROQUINE may also be subject to several of the known interactions of chloroquine even though specific reports have not appeared including reduction of the antibody response to primary immunization with intradermal human diploid cell rabies vaccine. |

APPENDIX C ORAL HYDROXYCHLOROQUINE ADMINISTRATION

Hydroxychloroquine should be taken with a meal or a glass of milk. Try to take your hydroxychloroquine at about the same time every day. Please record any side effects from the medication in the medication diary given to you by your study team.

- Use of nausea medicines (Phenergan, Compazine, or Zofran) may be helpful, and these medicines are best given about 30-60 minutes before the hydroxychloroquine. Please discuss this with your doctor.
- If you are unable to take the medicine, call your doctor for further instructions
- If you vomit within 30 minutes of taking the medicine, you may take a second dose of the medication. Do not take more than two doses of medication in the same day.
- If you vomit longer than 30 minutes after taking the medicine, do not take any more hydroxychloroquine that day.
- If you have any questions, call your doctor for further instructions.

| Common hydroxychloroquine side-effects | What can I do if I experience this? |
|--|--|
| Feeling sick, stomach pain, loss of appetite, diarrhea | Remember to take the tablets after food or with a drink of milk. Stick to simple foods - avoid spicy or rich meals |
| Headache | Ask your doctor or pharmacist to recommend a suitable painkiller |
| Eye problems (for example, blurred vision or sensitivity to light) | Let your doctor know about this as soon as possible |
| Skin rash or itching | If this becomes troublesome, speak with your doctor |

If you have any other symptoms which you think may be due to this medicine, speak with your doctor or pharmacist.

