5.2 Agent Administration

Treatment will be administered on an outpatient basis. Reported adverse events and potential risks are described in Section 7. Appropriate dose modifications are described in Section 6. No investigational or commercial agents or therapies other than those described below may be administered with the intent to treat the patient's malignancy.

| Dose Schedule | |
|------------------------|------------------------------------|
| Dose Level | Dose |
| | Hydroxychloroquine (mg/day) |
| Level -1 | 200 mg/day |
| STARTING DOSE: Level 1 | 400 mg/day |
| Level 2 | 800 mg/day |
| Level 3 | 1200 mg/day |

Subjects will receive HCQ every day for 14 days, starting at least 14d before planned surgery and optimally ending day prior to surgery. Dosing can be extended 7 days if necessary due to unexpected delays. HCQ can be taken at any time of the day with meals. Tablets of HCQ are available in 200 mg strengths. HCQ will be administered in divided doses (twice a day) for doses above 200 mg/day to minimize nausea. The divided doses should be taken in the AM and at night with meals. Subjects will also be required to keep a medication diary and to present this at the end of the treatment. Should a subject have emesis and regurgitate the medication within 30 minutes of taking it, the dose may be repeated once, but if vomiting occurs longer than 30 minutes after ingestion, the dose should not be repeated. Subjects taking antacids, proton-pump inhibitors or H2-blockers should not take hydroxychloroquine within 4 hours of these medicines.

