5.3 See Statistical Considerations for description of Dose-Escalation Process

An adaptive, nonparametric, isotonic regression model will be employed in order to determine the biological effect of HCQ as well as to assess safety. Patients will be enrolled starting at dose level 1. Dose escalation and de-escalation is described in detail in the Statistical Considerations section below. Briefly,

1. Treat a cohort of 3 patients at dose level 1
2. Let j^t denote the highest level tried thus far. At the current dose level j , based on the observed data, determine the dose j^* that has the highest isotonic estimate of biological effect probability among the tried doses.
3. If $j^* > j$, escalate to dose $j+1$
4. If $j^* < j$, de-escalate to dose $j-1$
5. If $j^* = j < j^t$, stay at dose level j ; otherwise if $j^* = j = j^t$, escalate to dose $j+1$

Once the maximum sample size is reached ($n = 18$), select the lowest dose that has the highest estimate of biological effect based on PAR-4 levels.

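### At Levels 1 to 3, the patient handout (Appendix C) cancels the scheduled night dose after late vomiting of the morning dose, while Section 5.2 only bars repeating the vomited dose

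*Combined protocol and SAP*

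**What the plan says.** Section 5.2 (Agent Administration) sets 200 mg/day at Level -1 and 400, 800 and 1200 mg/day at Levels 1, 2 and 3. On splitting it says "HCQ will be administered in divided doses (twice a day) for doses above 200 mg/day to minimize nausea" and "The divided doses should be taken in the AM and at night with meals". Levels 1 to 3 are therefore two intakes a day, and only Level -1 is a single intake. Section 5.3 adds "Patients will be enrolled starting at dose level 1", so divided dosing applies from the first patient.

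For a dose brought up within half an hour, and for later vomiting, Section 5.2 says "the dose may be repeated once, but if vomiting occurs longer than 30 minutes after ingestion, the dose should not be repeated". It sets no daily maximum and says nothing that cancels the next scheduled intake.

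Appendix C, addressed to the patient, instructs differently on late vomiting: "If you vomit longer than 30 minutes after taking the medicine, do not take any more hydroxychloroquine that day". After early vomiting it allows a second dose, and it then limits the patient to two doses a day without saying whether a dose is one intake or the daily amount.

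Section 5.2 also requires a diary: "Subjects will also be required to keep a medication diary and to present this at the end of the treatment". The Appendix D diary has 14 rows, one per day, with columns for date, time and side effects. It has no AM/PM split and no field for the amount taken. Section 5.2 allows a longer course than the diary covers: "Dosing can be extended 7 days if necessary due to unexpected delays".

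**The concern.** The body of the protocol and the patient handout give different instructions for the same event at every dose level except Level -1. Section 5.2 states "Treatment will be administered on an outpatient basis", so the handout is the rule the patient has at home. Following it drops a scheduled intake that Section 5.2 leaves in place.

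What is at stake is the dose actually delivered and the dosing history used in the exposure analysis. Section 2.4 expects PAR-4 secretion to follow exposure (area under the curve) rather than nominal dose. Section 11.6 plans a Bayesian forecast of each patient's HCQ exposure from limited sampling, and such a forecast depends on when and how much drug was taken. A night dose skipped on day 6 or day 13, just before a D7 or D14 draw, would make an assumed full dosing history wrong at the point where the samples inform the model. The diary is the only patient intake record that the documents show, and it does not ask for the second intake of the day.

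**Working it through.** The plan gives no figure to reproduce here. The check compares the two instructions and then sizes the difference.

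**Inputs.** Daily doses are 200, 400, 800 and 1200 mg, given twice daily above 200 mg, for 14 days with a possible 7-day extension (all Section 5.2). The handout rules are from Appendix C and the diary layout from Appendix D. Equal halves are forced at Level 1 by the 200 mg tablet and are assumed at Levels 2 and 3.

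**Step 1: late vomiting of the morning dose.** Under Section 5.2 the morning dose is not repeated and the night dose stays on the schedule. Under Appendix C nothing more is taken that day, so the night dose is lost. At Level -1 there is no night dose and the two rules agree.

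**Step 2: size of one lost intake.** Intake = daily dose / 2. Share of the course = 1 / (2 × days).

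| Level | mg/day | One intake (mg) | Share of day | 14-day course (mg) | Share of course |
|---|---|---|---|---|---|
| 1 | 400 | 200 | 50% | 14 × 400 = 5600 | 200/5600 = 3.6% |
| 2 | 800 | 400 | 50% | 14 × 800 = 11200 | 400/11200 = 3.6% |
| 3 | 1200 | 600 | 50% | 14 × 1200 = 16800 | 600/16800 = 3.6% |

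The share is 1 of 14 × 2 = 28 intakes. Over 21 days it is 1 of 21 × 2 = 42, or 2.4%.

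**Step 3: amount retained on that day.** Let f, between 0 and 1, be the fraction of the morning dose absorbed before vomiting, and suppose a night dose, if taken, is kept. Appendix C then gives 0.5f of the assigned daily dose, a range of 0 to 50%. Section 5.2 gives 0.5f + 0.5, a range of 50 to 100%. The difference is 50 percentage points whatever f is.

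**Step 4: early vomiting of the morning dose, repeated once.** Section 5.2 permits morning + repeat + night = 3 intakes swallowed (600, 1200 or 1800 mg at Levels 1, 2, 3). The Appendix C limit, read per intake, is reached after the repeat: 2 intakes (400, 800 or 1200 mg). The night dose is barred, so the loss is again one intake.

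**Step 5: diary.** There are 14 Time cells for 28 scheduled intakes, so 28 − 14 = 14 intakes have no cell of their own. If dosing is extended, the 7 × 2 = 14 intakes of days 15 to 21 have no row.

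**Frequency.** Section 7.3 lists vomiting as common (at least 1% and below 10%), but this is a general listing. It does not give the rate of late or early vomiting per dose in this trial, so an expected number of lost intakes cannot be computed.

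**The case against.** The best defence is that the handout may be deliberately cautious. Section 6.1 holds HCQ for vomiting of Grade 2 or higher, and a patient at home does not grade the event, so stopping for the rest of the day is a sensible default. Section 5.2 does not expressly address the next scheduled dose; that it stands is inferred from the twice-daily schedule. Appendix C also tells patients to call their doctor with questions. This may explain the wording, but it does not reconcile the two texts. If the stricter rule is intended, Section 5.2 should say so. A patient with a clear written instruction has little reason to call.

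The consequence is also small. The effect falls mainly on Grade 1 vomiting, because higher grades trigger a hold. The exposure model is informed by measured HCQ (three samples at each of D7 and D14, plus pre-study and post-operative draws), and histories are taken at D7 and D14. The eCRFs and data management plans are not shown and may capture more. Section 11.6 does not say that the diary supplies its dose input. All of this stands and limits the point.

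Three stronger readings are tempting but not supported:

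- A reader might infer that a day with a cancelled night dose looks the same in the diary as a normal day. The diary has a Side effects column and Appendix C asks patients to fill it in, so the vomiting would usually show. What is missing is a prompt for the time and amount of the second intake.
- A reader might take the two-dose limit as daily amounts and conclude that the handout authorises 800, 1600 or 2400 mg. The limit is a ceiling and does not grant permission. Section 5.2, which has no daily cap, reaches the same totals if both intakes are vomited early and each is repeated (4 × 200, 4 × 400, 4 × 600 mg).
- A reader might see the advice to keep to a regular time each day as proof that the handout was written for once-daily use. That advice fits fixed morning and night times equally well.

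**Conclusion.** The conflict is real and should be corrected. At Levels 1 to 3 the handout removes a scheduled night dose after late vomiting of the morning dose and, if its limit is read per intake, also after a morning dose is vomited early and repeated. Section 5.2 does neither. Each event removes 50% of that day's assigned dose and 3.6% of a 14-day course (2.4% of 21 days).

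The late-vomiting conflict rests on the plain wording of both texts. The early-vomiting part depends on reading a dose as one intake. The mg figures at Levels 2 and 3 assume equal halves, and the diary point assumes that the columns shown are the complete form.

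The effect is confined to delivered dose and to the input of the exposure model, and its frequency is unknown. A reader might infer that dose finding is compromised. The documents do not support that: no effect is shown on the sample size of 18, the operating characteristics in Table 1, or the PAR-4 responder analysis by dose level.

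**What to change.** Reword Appendix C to the per-dose rule of Section 5.2:

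- A dose vomited after 30 minutes is not repeated, and the next scheduled dose is taken unless the patient has been told to hold under Section 6.
- A dose vomited within 30 minutes may be repeated once, with any daily maximum stated in intakes or mg for the divided schedule.

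If the stricter rule is intended, amend Section 5.2 to say so instead.

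As a minor companion change, give the Appendix D diary separate AM and PM entries for time and tablets taken, for up to 21 days, to support the Section 11.6 exposure model.

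The cost is a revised handout and diary page with IRB review. No extra visits, samples or patients are needed.
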